### **9.1. Adverse Event**

Subjects with any AE(s), SAE(s), SAR(s), serious SAR(s) and ESI(s) will be tabulated for each actual treatment received. Besides the overall AE summary, subjects with any AE(s) will be tabulated by SOC and PT specified in MedDRA Version 20.0. Subjects with any AE(s) will also be tabulated by SOC, PT and maximum severity. A subject who experienced multiple AEs within a SOC or PT will be counted only once at the maximum severity for that SOC or PT. SAEs, SARs, and Serious SARs will be tabulated similarly.

Summaries for ocular AEs and non-ocular AEs will also be performed. Ocular AEs, ocular SAEs and ocular SARs will be summarized for study eyes and fellow eyes separately. Any ocular AE that occurred simultaneously to both eyes will be counted once for both the study eye and the fellow eye.

All AE tabulations will be performed on the Safety population for the On-treatment period, Follow-up period and entire study.

AEs, AEs leading to death, AEs leading to discontinuation, SAEs, and ESIs, if any, will be listed separately.

### **9.2. Slit-lamp Biomicroscopy**

Frequency and percentage of severity rating score will be summarized by actual treatment received and analysis visit for study eyes. In addition, subjects with any clinically significant worsening from baseline, defined as from normal to abnormal for iris and pupil, or worsening (increase) of 2 units or more for the rest biomicroscopy parameters, will be summarized and listed. For anterior chamber cells, rating score from 0 to 0.5 is considered as 1 unit of increase, and from 0 to 1 is considered as 2 unit of increase. The summaries of cataract severity score apply to phakic lens only.

For all biomicroscopy parameters, subjects with any worsening of 2 units or more after injection will be summarized and listed.

### **9.3. Ophthalmoscopy**

For cup to disc ratio, scores and changes from baseline will be summarized by actual treatment received and analysis visit for study eyes.

For binary ophthalmoscopy parameters (retina, macular and choroid), subjects with any change from Normal at baseline to Abnormal in status will be tabulated by actual treatment received and analysis visit for study eyes. In addition, a listing will be provided.

For vitreous haze, frequency and percentage of severity rating score will be summarized by actual treatment received and analysis visit for study eyes. In addition, subjects with worsening (increase) of 2 units or more from baseline will be summarized and listed.

For all ophthalmoscopy parameters, subjects with any worsening of 2 units or more after injection will be summarized and listed.

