7.5.4. Unscheduled Visits

If a subject requires evaluation between scheduled visits, complete all applicable study specified procedures as necessary and record the information on the Unscheduled Visit form(s).

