#### 4.1.5. Out-of-Window Measurements, Analysis Window and Analysis Visit

A measurement collected at a visit is an out-of-window measurement if the study day of the visit falls outside of a visit window specified in [Table 1](#), or a within-window measurement otherwise.

Analysis visit is a timing variable which will be used for all analyses involving visits. For each analysis visit, an analysis window is provided in order to determine which of the analysis visit a measurement should be mapped to. The analysis visit of a measurement will be determined by the study day of the measurement and the specified analysis windows. The study visit, assigned when the measurement was collected, will not necessarily agree with the analysis visit.

The following analysis windows for post-baseline visits will be applied to minimize the amount of missing data for analysis purposes:

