**Table 3: Post-Baseline Analysis Visit and Analysis Window**

Post-Baseline Analysis Visit (Target Assessment Date)	Visit Window	Analysis Window
Week 1 (Day 8)	[7, 9]	[2, 18]
Week 4 (Day 29)	[26, 32]	[19, 43]
Week 8 (Day 57)	[54, 60]	[44, 71]
Week 12 (Day 85)	[81, 89]	[72, 99]
Week 16 (Day 113)	[109, 117]	[100, 127]
Week 20 (Day 141)	[137, 145]	[128, 155]
Week 24 (Day 169)	[164, 174]	[156, 183]
Week 28 (Day 197)	[192, 202]	[184, 211]
Week 32 (Day 225)	[220, 230]	[212, 253]

For analyses involving post-baseline visits, if there are two or more measurements that fall into the same analysis window of a post-baseline visit, then the measurement at visit with any injection will be selected. If there is no visit with any injection, then the measurement closest to the target assessment day will be selected for that visit. In the case that two measurements are equidistant to the target assessment day, i.e., one is before and one is after the target assessment day, the later one will be selected for that visit.

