#### 4.3.5. Change and Percent Change from Baseline

The *change and the percent change from baseline* in a measure at a post-baseline visit will be defined as:

- Change = score at the post-baseline visit – baseline score.
- Percent change from baseline =  $100 \times \text{change} / (\text{baseline score})$

For any measure assessed pre and post injection at visits with injection(s), only the pre-injection scores at the visit will be used to derive the change-from-baseline variable.

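### Safety tables by analysis visit cannot show an unscheduled eye exam from Day 19 to Day 155 when the scheduled injection is given, because SAP 4.1.5 keeps one record per window and makes no exception for safety data

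*SAP*

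**What the plan says.** SAP 4.1.5 sets the scope: "Analysis visit is a timing variable which will be used for all analyses involving visits". Records are assigned by date: "The analysis visit of a measurement will be determined by the study day of the measurement and the specified analysis windows". An unscheduled exam therefore falls into a window like any other record.

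The selection rule under SAP Table 3 applies "if there are two or more measurements that fall into the same analysis window of a post-baseline visit". In that case, "then the measurement at visit with any injection will be selected". Only otherwise does distance matter: "If there is no visit with any injection, then the measurement closest to the target assessment day will be selected for that visit". There is no exception for safety measures and no worst-value rule, and the SAP does not mention unscheduled visits. Protocol 7.5.4 does provide for them, on their own form.

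For measures taken before and after an injection, SAP 4.3.5 adds that "only the pre-injection scores at the visit will be used to derive the change-from-baseline variable".

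The safety sections use the analysis visit unevenly:

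- **SAP 9.3, retina, macula and choroid:** "subjects with any change from Normal at baseline to Abnormal in status will be tabulated by actual treatment received and analysis visit", plus a listing.
- **SAP 9.4, IOP:** scores and changes by analysis visit, changes at 40 and 60 minutes after injection, and a listing of 60-minute rises. It has no summary of any elevation on other days.
- **SAP 9.2 and 9.3, slit-lamp and vitreous-haze scores:** by analysis visit.
- **SAP 9.2 and 9.3, worsening from baseline in slit-lamp items and haze:** summarized and listed, with no mention of analysis visit.

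**The concern.** Between injections, the scheduled eye exams are sparse. Injection 1 is followed by an exam at Week 1 (Visit 3). After injections 2 to 5 the next scheduled eye exam is the following monthly visit. Visit 10, one week after injection 6, has an AE query, a medication update, EKG and bloods but no eye exam (Protocol 7.5.2.10). A finding that appears and clears between monthly visits can therefore be graded only at an unscheduled visit. The protocol expects such visits, for example for IOP follow-up after an injection.

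A window rule meant to reduce missing data would then remove an observed abnormal exam in favour of a routine one. Safety is part of the primary objective. At stake are the arm-level counts of graded eye findings, above all a table that is worded as any change but built visit by visit.

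**Working it through.** **Inputs.** Target days, visit windows and analysis windows come from SAP Table 3. Injection visits (Day 1, Weeks 4, 8, 12, 16 and 20) come from SAP Table 1. The selection rule is that of SAP 4.1.5.

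**1. Reproduce the windows.** Each boundary should be the midpoint of neighbouring target days: (8+29)/2 = 18.5, (29+57)/2 = 43, (57+85)/2 = 71, (85+113)/2 = 99, (113+141)/2 = 127, (141+169)/2 = 155. Table 3 agrees. The five injection windows are contiguous: 25 + 4 × 28 = 137 days, Day 19 to Day 155. Every protocol visit window lies inside its analysis window.

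**2. Days after an injection that share its window.** Upper limit minus target day: 43−29 = 71−57 = 99−85 = 127−113 = 155−141 = 14 days, for 5 of the 6 injections. After injections 2 to 5, a later exam falls in the next injection window, where the next injection visit is preferred.

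**3. Apply the selection rule.** Take every scheduled day in the visit window with every other day in the analysis window as the unscheduled day. For Week 4 that is 7 × 24 = 168 pairs.

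| Window | Pairs | Unscheduled exam kept, injection given at scheduled visit | Unscheduled exam kept, no injection in window |
|---|---|---|---|
| Week 4 | 168 | 0 | 21 |
| Week 8 | 189 | 0 | 21 |
| Week 12 | 243 | 0 | 36 |
| Week 16 | 243 | 0 | 36 |
| Week 20 | 243 | 0 | 36 |
| Total | 1,086 | 0 | 150 |

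The middle result assumes no injection at the unscheduled visit. In the last column the closest-to-target rule decides, and the unscheduled exam is never kept when the scheduled visit is on target. These are counts of calendar combinations, not probabilities.

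**4. Outside Day 19 to Day 155.** With no injection visit in the window, closeness to target keeps 3 of 48 pairs at Week 1, 55 of 297 at Week 24, 55 of 297 at Week 28 and 55 of 451 at Week 32. Most unscheduled exams are dropped there too, but not all.

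**5. Illustration (assumed dates).** Injection on Day 57; unscheduled exam on Day 62 with an abnormal retina; normal again by Day 85. Days 57 and 62 both lie in [44, 71]. Week 8 keeps Day 57 and, under SAP 4.3.5, its pre-injection score, so the row shows the eye before the injection that preceded the finding. Week 12 is normal. The retina table never counts this subject.

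**6. Other routes into a table.** Change after injection (SAP 4.3.6) compares scores within one visit, and the slit-lamp and ophthalmoscopy post-injection exams are done within 30 minutes, so it cannot pick up Day 62. If DE-122 is withheld for raised IOP but Lucentis has been given, the visit still has an injection, so a later IOP check in that window is still displaced.

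**The case against.** The strongest reply is that little is lost from reporting as a whole.

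- SAP 9.2 and 9.3 provide listings, and Protocol 16.2 has all study parameters listed.
- Protocol 12.1.1 treats a significant adverse change from baseline as an AE. SAP 9.1 tabulates AEs by period, with no window selection and with study-eye events shown separately.
- A finding that persists is seen at the next monthly pre-injection exam.
- The worsening summaries for slit-lamp items, which include anterior chamber cells and flare, and for vitreous haze are not tied to analysis visit.

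All of this stands, and it limits the point. A reader might infer that graded inflammation drops out of the safety tables altogether. The documents do not support that: for the worsening summaries they leave open which records count. A reader might also infer that the exam tables would contradict the AE tables. They would not, because a by-visit row shows status at that visit and an AE may resolve between visits. Nor do the Stage 1 criteria in Protocol 7.4.1 depend on these tables. They concern six subjects up to Week 4 and are judged by the Safety Review Team.

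The reply does not dispose of the retina table or the IOP summaries. Listings give no counts by arm. AE severity is graded by interference with daily activities and need for treatment (Protocol 12.1.1.1), not by exam grade.

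**Conclusion.** The point holds for tables built by analysis visit: the retina, macula and choroid Normal-to-Abnormal table, the by-visit IOP summaries, and the by-visit slit-lamp and vitreous-haze scores. For the slit-lamp and haze worsening summaries it is an ambiguity to resolve, not a stated loss.

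It rests on two conditions: an injection is given at the scheduled visit, and none at the unscheduled one. Protocol Visit 8 allows DE-122 or sham to be given at a follow-up visit within the Visit 8 window. That can create two injection visits in one analysis window, which SAP 4.1.5 does not rank.

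The 137 days measure how long the rule operates, not how much information is lost. The documents give no rate of unscheduled visits or of transient findings. It is tempting to conclude that an excess of events on DE-122 would be biased toward zero. That would need more such events on DE-122, and nothing in the documents establishes this. The size and direction of any effect on the arm comparison are unknown. The change is still worth making, because the rule discards observed safety findings from an arm-level count and the correction is cheap.

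**What to change.** Keep the window rule for by-visit descriptive rows. Then:

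1. **SAP 4.1.5, 9.2 and 9.3:** state that every count of subjects with any worsening, or with a change from Normal to Abnormal, uses all post-baseline exams, scheduled and unscheduled, and counts each subject once in the On-treatment period and once in the Follow-up period. This resolves the slit-lamp and haze ambiguity and corrects the retina, macula and choroid table.
2. **SAP 9.4:** add each subject's maximum post-baseline IOP, excluding same-day post-injection readings, which already have their own summary.
3. **Alongside these counts:** show the number of unscheduled exams by arm.

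The cost is SAP wording, one derived subject-level record per parameter and one added IOP summary. No new data are needed. The downside is uneven ascertainment: subjects with more unscheduled visits have more chances to be counted. Item 3 lets the reader judge that.

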**Table 5: Safety Measures**

Safety Measure	Note
Intraocular pressure (IOP)	
IOP will be measured by applanation tonometry and reported in millimeters of mercury (mmHg). The IOP of an eye is derived as the mean/median of two or three consecutive IOP measurements.
 
IOP will be measured before Lucentis® and 40 (±10) minutes after Lucentis® injection. If applicable, IOP will be measured again 60 (±10) minutes following Lucentis® injection. Any increase of ≥ 10 mmHg in IOP at 60 (±10) minutes post-injection will be reported as an AE.
 
The procedure will be also applied for DE-122 or Sham injection, and any post IVT injection of rescue treatment.

Slit-lamp biomicroscopy findings: lid Redness lid edema conjunctival hyperemia conjunctival edema corneal edema anterior chamber cells anterior chamber flare iris pupil lens phakic lens severity	
Slit-lamp biomicroscopy will be performed prior to Lucentis® injection and within 30 minutes after DE-122 or Sham injection, and any post IVT injection of rescue treatment.
 
Anterior Chamber Cells will be graded as 0 = No cells, 0.5 = 1-5 cells, 1 = 6-15 cells, 2 = 16-25 cells, 3 = 26-50 cells, or 4 = >50 cells.
 
Anterior Chamber Flare will be graded as 0 = None, 1 = Faint, 2 = Moderate, 3 = Marked, or 4 = Intense.
 
The iris and pupil status of an eye will be graded as either normal or abnormal.
 
The lens of an eye will be classified as phakic, aphakic, or pseudophakic.
 
The rest biomicroscopy parameters will be graded as 0 = None, 1 = Mild, 2 = Moderate, or 3 = Severe.

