**Table 5: Safety Measures (Continued)**

Safety Measure	Note
Ophthalmoscopy findings: cup/disc ratio retina macula choroid vitreous	Indirect ophthalmoscopy will be performed prior to Lucentis ® injection and within 30 minutes after DE-122 or Sham injection, and any post IVT injection of rescue treatment.  Cup/disc ratio will be recorded with two decimal points (e.g., 0.80).  The retina, macula and choroid will be graded as either normal or abnormal.  Vitreous haze and opacification will be graded as: 0 = Clear Trace or 0.5+ = Trace 1+ = Few opacities, mild blurring 2+ = Significant blurring but still visible 3+ = Optic nerve visible, no vessels seen 4+ = Dense opacity obscures the optic nerve head.
Laboratory test: urinalysis hematology serum chemistry	Laboratory test results will be graded as: 1 = Normal 2 = Not Clinically Significant Abnormality 3 = Clinically Significant Abnormality 4 = No Results/Invalid Results 5 = Sample Not Collected  Refer to Section 23.4.16 of the protocol for the list of the minimum blood parameters and urine parameters.
Vital signs: systolic blood pressure diastolic blood pressure heart rate	Systolic blood pressure and diastolic blood pressure will be measured in mmHg. Heart rate will be measured by beats/minute. The average of two or three readings will be used.

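### The after-injection 2-unit rule in SAP 9.2 and 9.3 can never be met by 6 of the 16 examination items it covers, so that part of the safety output is empty by construction

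*SAP*

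**What the plan says.** SAP 9.2 ends: "For all biomicroscopy parameters, subjects with any worsening of 2 units or more after injection will be summarized and listed". SAP 9.3 ends: "For all ophthalmoscopy parameters, subjects with any worsening of 2 units or more after injection will be summarized and listed". SAP 4.3.6 defines change after injection as the post-injection score minus the pre-injection score at the same visit.

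SAP Table 5 gives the scales:

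- Iris and pupil: "The iris and pupil status of an eye will be graded as either normal or abnormal".
- Fundus items: "The retina, macula and choroid will be graded as either normal or abnormal".
- Lens status: "The lens of an eye will be classified as phakic, aphakic, or pseudophakic".
- Cup/disc ratio is recorded to two decimals.
- The other items are ordered grades.

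Protocol 23.4.7 and 23.4.9 describe the same two-level grading and define abnormal as the presence of a clinically significant abnormality.

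For change from baseline, both sections treat binary items separately. In 9.2, worsening is "defined as from normal to abnormal for iris and pupil", with the 2-unit threshold kept for the remaining parameters. In 9.3, for retina, macula and choroid, "subjects with any change from Normal at baseline to Abnormal in status will be tabulated". The only special unit definition is in 9.2: "For anterior chamber cells, rating score from 0 to 0.5 is considered as 1 unit of increase", with 0 to 1 counted as two units.

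**The concern.** A threshold of two units applied to a two-level item cannot be crossed. The baseline rules in the same two sections show that the authors knew these items were binary, but the after-injection sentences drop the distinction.

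The protocol schedules slit-lamp and indirect ophthalmoscopy shortly after every DE-122 or Sham injection, so the data for this output are collected on purpose. Three of the five ophthalmoscopy items (retina, macula, choroid) are where a posterior-segment finding would be recorded. If the rule is programmed literally, their rows are blank in every arm, and a blank row looks the same as a true absence of change. If the programmer improvises instead, the output departs from the SAP, and SAP section 1 requires deviations to be justified and documented in the study report.

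**Working it through.** The plan gives no figure to reproduce. The check is to take each item in SAP Table 5, find the largest worsening its scale allows, and compare it with 2. One grade step is counted as one unit. For the binary items this is an assumption, because the SAP gives them no numeric coding.

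**Slit-lamp, SAP 9.2 (11 items)**

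| Item | Scale | Largest worsening | Can reach 2? |
|---|---|---|---|
| Lid redness, lid edema, conjunctival hyperemia, conjunctival edema, corneal edema, phakic lens severity (6) | 0 to 3 | 3 | yes |
| Anterior chamber flare (1) | 0 to 4 | 4 | yes |
| Anterior chamber cells (1) | 0, 0.5, 1, 2, 3, 4 | 5 steps | yes |
| Iris, pupil (2) | normal/abnormal | 1 | no |
| Lens status (1) | three unordered classes | none defined | no unit |

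**Ophthalmoscopy, SAP 9.3 (5 items)**

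| Item | Scale | Largest worsening | Can reach 2? |
|---|---|---|---|
| Retina, macula, choroid (3) | normal/abnormal | 1 | no |
| Cup/disc ratio (1) | ratio, about 0 to 1 | about 1 | no |
| Vitreous haze (1) | 0, 0.5+, 1+, 2+, 3+, 4+ | 4 by number, 5 by step | yes |

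**Tally**

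- Can meet the rule: 6 + 1 + 1 + 1 = 9.
- Can never meet it: 2 + 3 + 1 = 6.
- No unit: 1.
- Total: 9 + 6 + 1 = 16 = 11 + 5.

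**Vitreous haze.** Section 9.3 does not say how the 0.5+ grade counts.

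- Six grades give 6 × 5 / 2 = 15 possible upward changes.
- By grade step, the changes of two or more number 4 + 3 + 2 + 1 = 10.
- By numeric value there are 8: 0–2, 0–3, 0–4, 0.5–3, 0.5–4, 1–3, 1–4 and 2–4.
- The two that differ are 0 to 1+ (1 by number) and 0.5+ to 2+ (1.5 by number).

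The same gap affects the from-baseline haze sentence in 9.3, which uses the same undefined unit.

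**Reach.** The output counts subjects, so it concerns at most 17 + 31 + 28 = 76. The number who could show a new change is smaller. Every study eye enters with active choroidal neovascularization (protocol 8.1), so the macula may often be abnormal already. The pupil is dilated before injection (protocol 10.6).

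**After the fix.** If normal-to-abnormal counts as worsening, one step is enough and all five binary items can be flagged.

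**The case against.** The strongest reply is that nothing clinically important is lost. Abnormal already means clinically significant. Protocol 12.1.1 makes a significant adverse change from baseline an adverse event, and the visit procedures require an adverse event assessment after each injection. SAP 9.1 tabulates ocular events for study eyes by actual treatment, and protocol 16.2 lists all study parameters. A reader might infer that post-injection retinal changes would go undetected. The documents do not support that, and this part of the objection stands.

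A reader might also infer that a post-injection change that clears by the next visit would appear in no examination summary, because SAP 4.3.5 uses only pre-injection scores at injection visits. That goes too far. Section 4.3.5 restricts the change-from-baseline variable, which is a score difference. The from-baseline tables for the binary items are status changes, and the SAP does not say that the restriction governs them. Such a change may be missed there, but no more than that can be said.

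It can also be said that the intent is plain from the baseline rules, so this is a drafting slip. That is fair as to cause. It does not make the sentences workable, since both say they apply to all parameters.

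Finally, the rule could work if normal and abnormal were coded at least two units apart, or if a smaller unit were set for cup/disc ratio. Neither document says so.

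**Conclusion.** The after-injection rule is wrong as written for 6 of 16 items: iris, pupil, retina, macula, choroid and cup/disc ratio. It is undefined for a seventh, lens status. It works for the nine graded scales, apart from the open question of how to count the 0.5+ haze grade, which decides 2 of 15 possible upward changes.

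The conclusion rests on reading a unit as one grade step, or as one on the recorded numeric scale for cup/disc ratio.

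Severity is minor. What fails is one supplementary descriptive examination summary in a study with no hypothesis test. The practical risk is that structurally empty rows are reported as if they showed no change.

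**What to change.** In the after-injection sentences of SAP 9.2 and 9.3:

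1. For iris, pupil, retina, macula and choroid, summarise and list subjects with any change from normal before injection to abnormal after it, by actual treatment in the Safety population. This extends the SAP's own from-baseline rule.
2. Limit the 2-unit rule to the nine graded scales.
3. Summarise cup/disc ratio as a numeric change after injection, and state that lens status is outside the rule and is listed only.
4. State one counting rule for the 0.5+ grade of vitreous haze and use it in both the from-baseline and the after-injection sentences of 9.3. Counting by grade step would match what 9.2 does for anterior chamber cells.
5. Add a footnote that, under protocol 9.4, post-injection examinations are done by unmasked staff, so the comparison between arms is descriptive.

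The cost is a few sentences in the SAP, one footnote and small programming changes. No new data are needed and no study procedure changes.
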